# 4.1.10. Rationale for Selection of Doses for this Study

As presented above, intranasal oxytocin has been studied in small clinical trials of patients with mental health disorders at doses ranging from 18 IU to 320 IU given as single doses or in divided doses given BID or QID for as long as 13 weeks. The 3 small randomized controlled trials examining the effects of intranasal oxytocin in patients with AUD reported by Pederson (*Pederson-2013*, *Pederson-2017*) suggested that intranasal oxytocin may attenuate alcohol withdrawal symptoms, reduce very heavy drinking, reduce anxiety scores, and can be safely administered at doses of 80 IU/day for 12 weeks. This Phase 2 trial proposes to study a dose of 70 IU/day in a larger group of patients, with a run-in period of 2-weeks of once-daily intranasal oxytocin at 35 IU, followed by 10-weeks of twice daily oxytocin at 35 IU for a total daily dose of 70 IU that is similar to the dose shown to be safe and effective in reducing drinking, craving, anxiety, and withdrawal by *Pederson* (2017).

# 4.2. Study Design

This study is a double-blind, randomized, placebo-controlled, parallel group, multi-site clinical trial designed to assess the efficacy of oxytocin compared with placebo to reduce drinking in 100 subjects (50 in each group) who report 4 or more Diagnostic and Statistical Manual of Mental Disorders − Fifth Edition (DSM-5™) symptoms of AUD. This study will be conducted at 4 clinical sites. If eligible for the study, subjects will be randomized using a stratified permuted block randomization procedure with "clinical site" as a stratification variable in an approximate 1:1 ratio (targeting 50 subjects per group) to receive either intranasal oxytocin or placebo for 12 weeks.

[figure not shown]
If eligible for the study, subjects will receive blinded intranasal oxytocin at 35 IU once-per-day or intranasal placebo (same volume once-per-day) for 2 weeks (initial tolerability assessment period), then for the next 10 weeks (maintenance period) subjects will receive oxytocin at 35 IU/BID, (total daily dose 70 IU) or intranasal placebo (same volume BID).

Subjects will be seen in the clinic at screening visit(s), at randomization (Week 1), and at Weeks 2, 3, 4, 6, 8, 10 and 13. During the alternate weeks when the subjects will not be coming into the clinic they will be contacted once during that week by telephone to encourage study drug compliance and to assess withdrawal, adverse events (AEs), and concomitant medications. A final follow-up telephone interview will occur during Week 14/15 (1-to-2 weeks after the end of dosing).

The overall study schema is provided in Figure 1. The study schedule of visits and assessments is shown in Table 3.

Enrollment will be halted if 2 or more at least possibly related SAEs as judged by the investigator or medical monitor occur. If this occurs, a DSMB will be convened and a decision in conjunction with the study Sponsor will be made regarding stopping the study.

Figure 1: Overview of Study Design

\*Telephone contact, otherwise visit is in clinic

 Table 3.
 Schedule of Assessments

	Screen						I	Mainte	enance					EOS a	Safety Follow-up
Study Week	-2 to -1	1	2	3	4	5	6	7	8	9	10	11	12	13	14/15
Clinic Visit #	1	2	3	4	5		6		7		8			9	
Informed Consent	X														
Alcohol Breathalyzer	X	X	X	X	X		X		X		X			X	
Urine Drug Screen b	X	X	X	X	X		X		X		X			X	
Locator Form	X														
Demographics	X														
Medical/Surgical History	X	$\mathbf{X}^{c}$													
Physical Exam	$\mathbf{X}^{\mathrm{d}}$	X	X	X	X		X		X		X			X	
MINI V 7.0.2 (AUD module at EOS)	X													X	
C-SSRS		X	X				X		X		X			X	
Clinical Chemistry e	X						X		X		X			X	
Vital Signs	X	X	X	X	X		X		X		X			X	
ECG (12-lead)	X													X	
Prior and Concomitant Meds	X	X	X	X	X	X	X	X	X	X	X	X	X	X	X
CIWA-AR	X	X	X	X	X		X		X		X			X	
Eligibility Checklist	X	X c													
Drug Compliance – Diary review		X	X	X	X		X		X		X			X	
Drug Accountability (vial weight)		X	X	X	X		X		X		X			X	
Pregnancy Test/Female Birth Control Methods	X	X	$\mathbf{X}^{\mathrm{f}}$				X		X		X			X	
Weight	X						X		X		X			X	
Drinking Goal	X														
AEs/SAEs			X	X	X	X	X	X	X	X	X	X	X	X	X
Other Services Used for Alcohol Use		X												X	
Problems g		Λ												Λ	
RANDOMIZATION		X													
Brief Telephone Interview h						X		X		X		X	X		
Take Control		X	X	X	X		X		X		X				
Exit Interview														X	
Treatment Referral														X	
Follow-Up Telephone Interview															X
Final Subject Disposition															X

	Screen						1	Mainte	enance					EOS a	Safety Follow-up
Study Week	-2 to -1	1	2	3	4	5	6	7	8	9	10	11	12	13	14/15
Clinic Visit #	1	2	3	4	5		6		7		8			9	
Subject Reported Outcomes															
Hyperkatefia Scale		X												X	
Barrett Impulsivity Scale		X													
Spielberger Trait Anxiety Inventory		X													
BPAQ - SF i		X					X		X		X			X	
Simplified Nutritional Appetite Questionnaire		X					X		X		X			X	
Cigarette and other nicotine use		X					X		X		X			X	
ECR-RS j		X					X		X		X			X	
IDS-30 k		X													
POMS		X					X		X		X			X	
PROMIS – alcohol negative consequences		X					X		X		X			X	
PROMIS – sleep disturbances		X					X		X		X			X	
PROMIS – pain interference		X					X		X		X			X	
UPSIT 	X			X			X		X		X			X	
Urge to drink questionnaire		X					X		X		X			X	
Timeline followback (TLFB)	X	X	X	X	X		X		X		X			X	
Brief Drinking Questionnaire m														X	

<sup>a EOS=end of study. These assessments are to be done at Week 13 or if the subject discontinues early and agrees to a final clinic visit.

<sup>b Test for opioids, cocaine, amphetamines, methamphetamine, THC, buprenorphine, methadone, benzodiazepines, oxycodone, 3,4-methylenedioxymethamphetamine (MDMA), and barbiturates.

<sup>c Updated prior to randomization.

<sup>d Complete physical exam at screening including examination of the nares, plus examination of the nares at all other visits as indicated.

<sup>e AST, ALT, total bilirubin, creatinine, sodium, and potassium.

f Only birth control methods are collected at this visit.

<sup>g At baseline asks about lifetime treatment use and at EOS asks "since beginning this study

<sup>h AEs, concomitant medications, and drug compliance reminder.

<sup>i Buss Perry Aggression Questionnaire – Short Form

<sup>j Experiences in Close Relationships—Relationship Structures Questionnaire (ECR-RS) (attachment related anxiety)

<sup>k Inventory of Drinking Situations

<sup>1 University of Pennsylvania Smell Identification Test

<sup>m Only asked to subjects who request to withdraw from the study and are not willing to provide TLFB drinking data. This questionnaire will be asked at whatever constitutes the EOS visit.

### 4.3. Benefit/Risk Assessment

Intranasal oxytocin is remarkably well tolerated and 80 IU per day has been administered for up to 13 weeks in two studies (*Ohlsson-2005*, *Pederson-2017*). Infrequent hyponatremia, probably secondary to an anti-diuretic effect, and infrequent nasal irritation have resulted in cessation of treatment. To minimize this risk, patients with significant gastrointestinal, cardiac, neurological, and renal disorders as well as pregnant or lactating women will be excluded. Sodium levels in addition to other liver enzyme and creatinine levels will be monitored over the course of treatment. A physical examination of the nares and throat will also be performed for signs of irritation; and sense of smell will be regularly evaluated. Dose reductions are permitted in the event of intolerance. The benefit of participating in this study is that all subjects will be asked to view the "Take Control" behavioral platform. The intervention is derived from a self-help approach developed by NIAAA that provides evidence-based, field tested information for individuals with alcohol problems, and suggestions for making changes in their drinking. In addition, it is possible that subject randomized to receive Oxytocin nasal spray may reduce their alcohol drinking which can have positive overall health benefits.

NCIG, NIAAA, NIH

Oxytocin for Alcohol Use Disorder Protocol Number: NCIG-007R

# 5. Study Objectives

# 5.1. Primary Objective

The primary objective of the study is to compare the efficacy of oxytocin in reducing the weekly percentage of heavy drinking days over 10 weeks of maintenance treatment among subjects with moderate to severe AUD. A "heavy drinking day" is 4 or more drinks per drinking day for women and 5 or more drinks per drinking day for men.

# 5.2. Secondary Objective

Secondary objectives include assessment of other measures of the effects of oxytocin compared with placebo on reduction of alcohol use as well as effects on alcohol craving, alcohol-related consequences, cigarette smoking and other nicotine use, psychological assessments, retention in the study, and safety and tolerability throughout the study.

# 6. Study Interventions

# 6.1. Investigational Products: Oxytocin and Placebo

Investigational products will be manufactured under contract with University of Iowa and will be packaged and distributed in drug kits by Catalent, Inc. Oxytocin and Placebo liquid formulations will be packaged in 20 mL vials with a fill volume of 18 mL with a Nemera P270 pump spray actuator device crimped to the vial. Oxytocin is supplied at a concentration of 70 IU/mL. The pump spray actuator delivers  $100 \, \mu L$  in a single spray (equivalent to 7 IU of oxytocin).

Oxytocin and placebo will be administered once daily (morning) for 2 weeks (Weeks 1 and 2) and then twice daily (morning and evening) for 10 weeks (Weeks 3 through 12). One dose is defined as the intranasal administration of  $100~\mu L$  per each nostril for a total of 5 insufflations alternating between nostrils with a 30 second wait between insufflations for a total dose of 500  $\mu L$  equivalent to 35 IU. Thus, subjects will receive oxytocin 35 IU per day for 2 weeks, then 35 IU twice per day for 10 weeks for a total daily dose of oxytocin 70 IU.

# 6.2. Investigational Product Packaging, Labeling, and Distribution of Drug Kits

Investigational products will be provided in drug kits containing 6 bottles of either oxytocin or placebo in each kit with each bottle containing 18 mL of oxytocin or placebo. Kits will be shipped periodically to sites during the study depending on enrollment.

The study number and the words "oxytocin or placebo study" will be preprinted on each vial label. The label will also have a unique kit number, the volume contained in the bottle, storage conditions, and the words "Caution: New Drug – Limited by Federal (or United States) Law to Investigational Use" and "Keep Out of Reach of Children". A separate label will be supplied to affix to the vial each time a bottle is dispensed. This label will contain the clinical site name, clinical site phone number and 24/7 emergency phone number, and places to record the subject number and the date dispensed.

### 6.3. Investigational Product Storage

Kits should be stored under refrigeration (within the range of 36°F to 46°F; 2°C to 8°C) in a secured area at the clinical site. After dispensing subjects will be instructed to store the vials under refrigerated conditions; however, stability at room temperature (68°F to 77°F; 20°C to 25°C) has been demonstrated for one month, so excursions to room temperature for 30 days or less should not impact the product.

# 6.4. Investigational Product Dispensing

Prior to dispensing the study drug vials, each vial will be weighed on an analytical balance that measures to the 0.01g or lower level and the weight will be recorded. The person dispensing the drug will prime the pump by depressing the actuator 5 times and will weigh the vial again. This will be done each time a new vial is dispensed. Repriming of the pump between uses is not necessary.

The subject will be instructed to return study vials at each clinic visit. Upon return of the used study drug vial, the vial will be weighed a second time to estimate the amount of drug insufflated

during the dosing period. Bottle weights will be collected at each visit when the subject returns the vial.

Dispensing will be in accordance with the plan in Table 4, unless the subject does not return within the scheduled windows around visits, then other arrangements can be made. Vials contain sufficient volume of investigational product in one vial for 16 to 17 days of dosing at 2 doses per day. As the first two weeks are one per day dosing, then vial #1 will have enough for the first two weeks, plus approximately another 7 days at twice daily dosing. Vial #1 can serve as a backup if needed. When vials are dispensed, the subject will be provided with a card that shows which numbered vial to use over the date range covered by the amount in the vial.

Table 4:	Investigational Product	Dispensing Plan

Study Week a	Vial # Dispensed	Vial #s Returned
1	1	NA
2	1	1 (weighed and redispensed)
3	2	1 (weighed)
4	2+3	2 (weighed and redispensed)
6	4	2 + 3 (weighed)
8	5	4 (weighed)
10	6	5 (weighed)
13	NA	6 (weighed)

<sup>a Only weeks where clinic visits are scheduled are shown.

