### 6.7. Investigational Product Administration

To control dosing and absorption of investigational product, subjects will be instructed to administer the nasal spray with their head in an upright position closing one nostril with one finger while administering the spray in the other nostril and sniffing during administration. At the first administration on Study Day 1, subjects will be provided with instruction on how to self-

administer their first dose, will be observed while administering the first dose, and will be given an instruction sheet to take home. At subsequent visits, subjects will be asked to return the nasal spray devices.

*Missed Doses:* Subjects will be instructed if the dose is not taken at the recommended time, to skip this dose, and the next dose should be taken at the time of next scheduled dose; doses should never be doubled up.

**Dose Reductions and Discontinuation.** If the subject is not tolerating the investigational product, the dose can be reduced by 14 IU or 200 μL increments per dose (2 less sprays) to determine if the subject can tolerate a lower dose. For example, one spray in each nostril can be omitted for each reduction. Then the subject should try to continue to give one dose in the morning and one dose in the evening if during the maintenance period. If the dose is reduced during the initial 2-week tolerability period, then subjects will not escalate to the maintenance dose and will stay at the tolerated dose. If the subject develops a medical condition requiring discontinuation of the investigational product, he/she can simply discontinue immediately. In the event that a female subject becomes pregnant, she will be instructed to discontinue taking the investigational product immediately.

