If possible, clinic visits should be scheduled on the same day of the week that the subject received the first dose of study drug, but a 3-day window is allowed for conducting visits within the scheduled study week. Visits may be scheduled and conducted on any day of the week. Visits can be conducted outside of the scheduled study week, but only based upon subject request (e.g., for reasons related to patient non-compliance with the study schedule). Each subject will receive a visit schedule to take home for future reference.

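### Table 4 dispenses one vial at Week 10 for up to 21 days of twice-daily dosing, so a fully compliant full-dose subject runs out 1–5 days early unless the optional backup vial is given

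*Protocol*

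**What the plan says.** Protocol 6.1 sets maintenance dosing as "twice daily (morning and evening) for 10 weeks (Weeks 3 through 12", and Protocol 7.8 places the Week 13 visit after the last dose. Weeks 11 and 12 are telephone contacts.

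Protocol 6.4 makes the table the rule for subjects who keep to the visit windows: "Dispensing will be in accordance with the plan in Table 4, unless the subject does not return within the scheduled windows around visits". It gives the capacity: "Vials contain sufficient volume of investigational product in one vial for 16 to 17 days of dosing at 2 doses per day". It estimates about 7 days of twice-daily drug left in vial 1 after the first two weeks and adds "Vial #1 can serve as a backup if needed". Each time vials are dispensed, the subject receives "a card that shows which numbered vial to use over the date range covered by the amount in the vial".

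In Table 4, the Week 10 row dispenses vial 6 and takes vial 5 back to be weighed. The Week 13 row expects only vial 6. Where a returned vial is meant to go out again the table says so, as in the Week 4 row: "2 (weighed and redispensed". Neither vial 5 at Week 10 nor vial 1 at Week 3 carries that mark.

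On timing, Protocol 7.7 prefers visits on the weekday of the first dose, and "a 3-day window is allowed for conducting visits within the scheduled study week".

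**The concern.** Weeks 10 to 12 contain 21 dosing days and no scheduled clinic visit after Week 10, yet the table supplies a single vial that by the protocol's own figure cannot last that long. The other three-week run at full maintenance dose, from the Week 3 visit to the Week 6 visit, is given two vials.

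If sites follow the table literally, adherent subjects run out in Week 12. That week is in the primary analysis period (SAP 9.4.1), and SAP 9.7 compares compliance between arms week by week. A supply limit would then be recorded as non-adherence, and some of the final week would be observed off drug.

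**Working it through.** **Inputs**
- Fill 18 mL per vial; 0.1 mL per spray; 5 sprays (0.5 mL) per dose; twice daily, so 1.0 mL/day (Protocol 6.1).
- Priming 5 sprays = 0.5 mL per new vial (Protocol 6.4).
- Clinic visits at Weeks 1, 2, 3, 4, 6, 8, 10 and 13 (Protocol 4.2).
- Nominal visit day = 7 × (week − 1) + 1, so Week 10 starts on Day 64 and Week 13 on Day 85.

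**Reproducing the stated capacity.** (18 − 0.5) / 1.0 = 17.5 days. The stated 16–17 days leaves 0.5–1.5 mL in the vial, a plausible undeliverable residue. The stated figure is sound and is used below.

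**Days needed after Week 10.** 84 − 64 + 1 = 21 days, or 21 mL. That exceeds even the unprimed 18 mL fill.

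**Gap by visit day.** The window is read as Days 64–67, because Day 64 is the first day of the scheduled study week. Drug is assumed available up to the visit. Gap = days needed − (16 to 17). Week 12 is Days 78–84, 14 doses.

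| Week 10 visit | Days needed | Gap (days) | Week 12 doses available | Highest Week 12 compliance |
|---|---|---|---|---|
| Day 64 | 21 | 4–5 | 4–6 | 29–43% |
| Day 65 | 20 | 3–4 | 6–8 | 43–57% |
| Day 66 | 19 | 2–3 | 8–10 | 57–71% |
| Day 67 | 18 | 1–2 | 10–12 | 71–86% |

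At the theoretical 17.5 days per vial the gaps are 3.5, 2.5, 1.5 and 0.5 days.

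**Overall compliance.** Prescribed doses are 14 + 140 = 154. A Day 64 visit loses 8–10 doses: 144/154 to 146/154 = 93.5–94.8%. A Day 67 visit loses 2–4 doses: 150/154 to 152/154 = 97.4–98.7%.

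**Share of maintenance at the maximum.** 4/70 = 5.7% to 5/70 = 7.1%.

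**Who is affected (Day 64 visit).** Vial 6 holds 32–34 of the 42 doses due, so only subjects taking more than 32/42 = 76% to 34/42 = 81% of them run out. A dose reduced to 3 sprays needs 3 × 0.1 × 2 × 21 = 12.6 mL and fits one vial.

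**Which second vial would close the gap**
- Vial 5 remainder: Days 50–84 are 35 days; vials 5 and 6 hold 32–34. Still 1–3 days short.
- Vial 1: about 7 days as stated. By dose count it is (32 − 14)/2 = 9 to (34 − 14)/2 = 10 days. Enough either way.
- Vial 3 remainder: vials 2 and 3 hold 32–34 days and Days 15–35 use 21, leaving 11–13 days. Enough.

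**Total supply.** The kit holds 6 × 18 = 108 mL. Use is 154 × 0.5 = 77 mL in doses plus 6 × 0.5 = 3 mL priming, 80 mL in all. The problem is allocation, not quantity.

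**The case against.** The strongest reply is that the text and Table 4 are one plan. The paragraph above the table states the capacity, works out the spare drug in vial 1 and permits its use, and about 7 days covers every gap in the working. The missing redispensing mark for vial 1 cannot bar a use the text expressly allows. The vial card, completed on Day 64, would show vial 6 ending on Day 79 or 80, so staff should notice before the subject leaves. The Week 11 call checks dosing before run-out. Protocol 7.8 permits extra visits, Protocol 10.10 provides replacement vials, and the diary for bottles 2–6 does not tie a date to one vial.

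Much of this stands. If vial 1 goes out at Week 10, nothing is lost. The 29–43% figure is a ceiling for one case (Day 64, full dose, no backup), not an expectation. The Weeks 3–5 comparison is also imperfect, because a Week 4 visit falls inside that stretch.

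None of these provisions schedules a second vial, however. The backup is left to discretion, although for an on-schedule, fully compliant, full-dose subject the need is certain. Table 4 has vial 1 returned at Week 3 without redispensing it. The other arrangements in Protocol 6.4 are for subjects outside the visit windows. The extra visits are for subject concerns, missed visits, changes in health or circumstances, and repeat laboratory tests; the replacement vials are for pump failure. The card and calls can expose the gap but do not fill it. Missed doses are also not made up later: "doses should never be doubled up".

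**Conclusion.** The point holds, as a minor one. The stated vial capacity is right and the Week 10 row is short: by 4–5 days on the nominal schedule and 1–2 days for a visit at the end of the window. The lower end of the 1–5 day range therefore depends on a late visit.

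The result rests on full dose, near-complete adherence after Week 10, 16–17 days per vial, the Day 64–67 reading of the window, and no backup vial being given. The protocol does not say explicitly that its 3-day window runs only later.

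Both arms are supplied identically, so the consequence is lower Week 12 compliance in each and at most slight dilution of the treatment effect. There is no bias towards oxytocin, and the primary comparison is not threatened.

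**What to change.** Amend the Week 10 row of Table 4 to dispense vial 6 together with a named part-used vial that holds enough, for example vial 1 or the remainder of vial 3, marked as redispensed. Amend the Week 13 return row to list both vials, and update the subject's vial card to match. The sponsor should choose the vial, since Protocol 6.3 gives storage conditions but no limit on how long an opened vial may be used. Redispensing vial 5 alone would not be enough.

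The cost is an edit to two table rows and one card, with no extra product. If dosing is already complete, check the dispensing records for a second vial at Week 10 before interpreting Week 12 compliance.

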# 6.5. Investigational Product Accountability and Compliance

The site principal investigator (PI) or designated study personnel will maintain a log of the receipt of all investigational products and record of dispensing of all investigational products to the subject. Investigational product for each subject will be inventoried and accounted for throughout the trial. The site PI or his/her staff will count the drug kits/individual vials remaining at the end of the study and record the vial count on the appropriate drug accountability form. Subjects will be asked to return any used and/or unused vials of investigation product at each clinic visit for accountability. Subjects will be provided with a Diary Card (Appendix A) to complete each time they self-administer a dose and will be asked to bring the card back at each clinic visit for site staff to review and confirm dosing compliance.

# 6.6. Used/Unused Investigational Product Supplies

Unused investigational products will be retained at the clinical sites until the end of the study, at which time they will be shipped back to Catalent for destruction.

